#### 4.4.4 Reimbursement

Will subjects be reimbursed for their expenses, such as travel, parking, meals, or any other study related costs?

Yes  No

## 5 Study Design

### 5.1 Study Timelines

#### Part 1

As many as eighty healthy volunteers will be screened, with the goal of enrolling seven volunteers into Part 1 of the study, and six finishing the study. Each subject will be administered the same three treatments (thiamine only, thiamine and metformin combination, and thiamine and trimethoprim combination), simply in a different order, depending on his/her group assignment. There will be three cycles in this study, each separated by at least 5 days but no more than two weeks, unless previously approved by principal investigator. Subjects will be assigned to the treatments in a random order. Subjects will come three times during each cycle in which they will receive drug, vitamin, or a combination of the two and will be evaluated through multiple blood samples and urine collection.

Screening data, including the MRU Nursing Health History Questionnaire (see IRB submission #6701), urine sample, and a blood sample, will be reviewed to determine

subject eligibility. Subjects who meet all inclusion criteria and none of the exclusion criteria will be entered into the study.

Subjects will be randomized into one of three groups and will be administered a different sequence of drugs dependent on their group assignment:

Group 1: 5mg thiamine only (Cycle 1), 5mg thiamine and 1000mg metformin (Cycle 2), 5mg thiamine and 300mg trimethoprim (Cycle 3)

Group 2: 5mg thiamine and 1000mg metformin (Cycle 1), 5mg thiamine and 300mg trimethoprim (Cycle 2), 5mg thiamine only (Cycle 3)

Group 3: 5mg thiamine and 300mg trimethoprim (Cycle 1), 5mg thiamine only (Cycle 2), 5mg thiamine and 1000mg metformin (Cycle 3)

Despite the different sequence order, administration and sample collection for both drugs will remain the same for each group. Subjects will arrive on Day 0 of each cycle to pick-up three thiamine deficient meals (prepared by the site) that they will be asked to consume throughout the day without any other food intake. Female subjects will be asked to provide a urine sample to ensure non-pregnant status. On Day 1, subjects will arrive following an overnight fast and will be asked to complete a fasting weight, vitals, and a RN-administered health history questionnaire to review any change in medications or health status. Subjects will then be asked to empty their bladders and provide a baseline blood sample before being administered any drug(s). Subjects will receive vitamin or a combination of vitamin and drug. Subjects will be provided limited water, less than 500mL, following the dose and will be given no food or additional water for 4 hours post-dose to avoid excessive dilution of the dose or a food-drug interaction. After the 4-hour period, subjects will be provided their first meal and water ad libitum. Blood and urine collection will proceed on Day 1 as outlined below in Schedule of Study Outcomes. Subjects will be provided three thiamine deficient meals during their visit on Day 1. Subjects will be permitted to leave after the 12-hour post-dose sample collection and will be asked to fast overnight. On Day 2 of each cycle, subjects will arrive at the site, submit their urine collection kit, and have one more blood collection (24-hour post-dose). They will then be served a light standard breakfast. See Schedule of Study Outcomes for more details.

Total duration of the study including time to achieve complete enrollment and complete 9 study visits will be approximately 19-37 days depending on when the subject schedules their next cycle visit.

All subjects will provide at most 157.5mL of blood per cycle. Since the common standard for collection is approximately 1 pint (i.e. 473mL) at blood drives and/or donation centers, we feel that we will not putting the subject in danger. Loss of 550mL is not harmful and is typically replenished by the body within two to three weeks.

**Cycle Schedule (Repeat for a total of three cycles – 9 total visits)**

Visit	Activities	Expected Duration
Day -1 to 0 (Day -1 to 0)	-Consent (cycle 1 only) -Randomization -Pregnancy test for females -Weight, vitals (cycle 1 only) -Health/med/AE review -Meet with RD -Breakfast on site (optional)	1-2 hrs

	
 
-Pick-up study meals to be consumed the rest of the day (or following day)
 
-Fast overnight for 8 hours
 
	
Day 1	
 
-Vitals measured
 
-Health/med/AE review/
 
-Baseline urine sample
 
-Drug/vitamin administration
 
-Blood collections, drawn from IV (0h, 0.25h, 0.5h, 1h, 1.5h, 2h, 2.5h, 3h, 3.5h, 4h, 6h, 8h, 10h, 12h)
 
-Urine collections (0-4 h, 4-8 h, 8-12 h)
 
-Consume study diets
 
-Instructions for urine and fasting overnight
 
	14 hrs
Day 1 Overnight	-Urine Collection at Home (12-24 h)	
Day 2, 24-hours post-dose	
 
-Arrive fasting
 
-Submit urine kit
 
-Blood collection (24-hr post-dose)
 
-Urine collection (if necessary)
 
-Eat a standard breakfast
 
	1 hr
Washout (5-14 Days) between Cycle 1 and 2 and between Cycle 2 and 3	
 
-No visit required
 
-Resume usual diet
 
-Complete two food diaries
 
	20-30 minutes

## Part 2

Based on the results from Part 1, trimethoprim will be taken forward in a two-arm, randomized crossover design in Part 2 as follows:

After screening 60 volunteers, 14 subjects are expected to be enrolled at the Tufts site with the goal of having 12 healthy volunteers complete the study. Each subject will be administered the same two treatments (thiamine only and a combination of thiamine + trimethoprim), simply in a different order depending on arm assignment. There will be two cycles in this study, each separated by at least 5 days. Subjects will come in three times within a 72-hour period during each cycle.

Screening data, including a background questionnaire, urine sample, and a blood sample, will be reviewed to determine subject eligibility. Subjects who meet all inclusion criteria and none of the exclusion criteria will be entered into the study.

Subjects will be randomized into one of two groups and will be administered a different sequence of treatments dependent on their group assignment:

Group 1: thiamine only (Cycle 1), thiamine and trimethoprim (Cycle 2)

Group 2: thiamine and trimethoprim (Cycle 1), thiamine only (Cycle 2)

Subjects will arrive on Day 0 of each cycle to pick-up three thiamine deficient meals (prepared by the site) that they will be asked to consume throughout the day without any other food intake. Female subjects will be asked to provide a urine sample to ensure there is no change in pregnancy status. On Day 1, subjects will arrive following an overnight fast and will be asked to complete a fasting weight, vitals, and a RN-administered health history questionnaire to review any changes in medications or health status. Subjects will

then be asked to empty their bladders and provide a baseline blood sample before being administered any drug(s). Subjects will receive vitamin or a combination of the drug + vitamin. Subjects will be provided limited water, less than 500mL, following the dose and will be given no food or additional water for 4 hours post-dose to avoid excessive dilution of the dose or a food drug interaction. After the 4-hour period, subjects will be provided a naturally thiamine deficient snack and water ad libitum. Blood and urine collection will proceed on Day 1 as outlined below in Schedule of Study Outcomes. Subjects will be provided thiamine deficient snacks and one thiamine deficient meal during their visit on Day 1. Subjects will be permitted to leave after the 10-hour post-dose sample collection and will be asked to fast overnight. On Day 2 of each cycle, subjects will arrive at the site, submit their urine collection kit, and have one more blood collection (24-hour post-dose). See Schedule of Study Outcomes for more details.

Total duration of subject participation will be approximately 6 days. Total duration of the study will include time to achieve complete enrollment plus 11-20 days of the study depending on when the subject schedules their next cycle visit.

Cycle Schedule (Repeat for a total of two cycles – 6 total visits)

Visit	Activities	Expected Duration
Day -1 to 0	
 
-Consent (cycle 1 only)
 
-Randomization
 
-Pregnancy test for females
 
-Weight, vitals (cycle 1 only)
 
-Health/med/AE review
 
-Meet with RD
 
-Breakfast on site (optional)
 
-Pick-up study meals to be consumed the rest of the day (or following day)
 
-Fast overnight for 8 hours
 
	1-2 hrs
Day 1	
 
-Vitals measured
 
-Health/med/AE review
 
-Baseline urine sample
 
-Drug/vitamin administration
 
-Blood collections, drawn from IV (0h, 0.25h, 0.5h, 1h, 1.5h, 2h, 2.5h, 3h, 3.5h, 4h, 6h, 8h, 10h)
 
-Urine collections (0-4 h, 4-8 h, 8-10 h)
 
-Consume study diet
 
-Instructions for urine and fasting overnight
 
	12 hrs
Day 1 Overnight	
 
-Urine Collection at Home (10-24 h)
 
	
Day 2, 24-hours post-dose	
 
-Arrive fasting
 
Weight, vitals (cycle 2 only)
 
-Submit urine kit
 
-Blood collection (24-hr post-dose)
 
-Urine collection (if necessary)
 
-Eat a standard breakfast
 
	1 hr
Washout (5-14 Days) between Cycle 1 and 2	
 
-No visit required
 
-Resume usual diet
 
-Complete two food diaries
 
	

For Part 1, blood will be collected pre-dose as well as at 0.25, 0.5, 1, 1.5, 2, 2.5, 3, 3.5, 4, 6, 8, 10, 12, and 24 hours after the start of dosing for each cycle. For Part 2, blood will be collected pre-dose as well as at 0.25, 0.5, 1, 1.5, 2, 2.5, 3, 3.5, 4, 6, 8, 10, and 24 hours after the start of dosing for each cycle. Subjects will be asked to collect all urine samples during their stay in intervals of 0-4, 4-8, 8-12, and 12-24 (home kit) hours for Part 1 and 0-4, 4-8, 8-10, and 10-24 (home kit) hours for Part 2 respectively.

It is estimated that it will take approximately 1.5 to 2 years to complete this study.

## 5.2 Procedures

- Is there a placebo control arm?

Yes  No

Subjects will be screened using a screening questionnaire as well as by providing a blood and urine sample to determine eligibility. A screening informed consent will be completed at the beginning of the screen visit. Both the questionnaire and samples collected at screening will help monitor subjects for safety by identifying any risks before enrolling the subject into the study. Both drugs used in this study are FDA-approved. Metformin is an orally prescribed drug that is used as a first line of therapy for Type II diabetes patients and trimethoprim is a synthetic antibacterial that is commonly prescribed for urinary tract infections. All information will be collected on screening questionnaires and case report forms (CRFs).

Pregnancy tests will be conducted at screening and at each visit for women of reproductive potential. Women of reproductive potential will be instructed to use a birth control method of their choosing including but not limited to oral contraceptives, condoms, and IUDs. Men of reproductive potential will also be instructed to use a birth control method of their choosing including but not limited to condoms.

All procedures are being performed for research purposes and are not part of the usual standard of care at Tufts.

## 5.3 Evaluations

Will you perform any laboratory tests for this study?

Yes  No

## SCHEDE OF STUDY OUTCOMES

	SCREENING (Before Cycle 1 Day 1)	VISIT 1 (Cycle 1 Days 0 - 2)	VISIT 2 (Cycle 2 Days 0 - 2)	VISIT 3 (Cycle 3 Days 0 - 2)*
Informed Consent	X			
Health History Questionnaire	X			
CBC, metabolic panel	X			
Height	X			
Weight	X	X		
Vital Signs a	X	X	X	X
Pharmacokinetic blood sampling b		X	X	X
Pharmacokinetic urine collection c		X	X	X
Urine collection/Urinalysis	X	X	X	X
Pregnancy Test (Serum)	X			
Pregnancy Test (Urine)		X	X	X
Administration of Study Drug d		X	X	X
Initiate Subject Food Diary		X	X	
Subject Food Diary Collection			X	X
Concomitant Medication Review	X	X	X	X
Adverse Events		X	X	X

\*Visit 3 is only included in Part 1 of the study.

a Weight will be assessed only on Visit 1 of Cycle 1.

b Pharmacokinetic blood samples will be collected at pre-dose as well as at 0.25, 0.5, 1, 1.5, 2, 2.5, 3, 3.5, 4, 6, 8, 10, 12, and 24 hours post-dose at Visits 1, 2, and 3 for Part 1. Pharmacokinetic blood samples will be collected at pre-dose as well as at 0.25, 0.5, 1, 1.5, 2, 2.5, 3, 3.5, 4, 6, 8, 10, and 24 hours post-dose at Visits 1 and 2 for Part 2.

c Pharmacokinetic urine samples will be collected in intervals of 0-4, 4-8, 8-12, and 12-24 hours at each visit/cycle for Part 1. Pharmacokinetic urine samples will be collected in intervals of 0-4, 4-8, 8-10, and 10-24 hours at each visit/cycle for Part 2.

d Administration of study drug will be dependent on which group the subject is enrolled in and will be either thiamine only, thiamine + metformin combination, and/or thiamine + trimethoprim combination depending on the cycle/visit/part of the study.

Subjects will be sampled at screening and during Part 1 & 2 at Cycle 1, 2, & 3 (for Part 1) on both Days 1 and 2. All laboratory tests that will be performed comply with the Clinical Laboratory Improvement Amendments of 1988. Details of the analyses are described below.

**Screening Laboratory Tests:**

During the screening visit, 20 mL of blood will be collected for standard health screen, complete blood count with differential and routine clinical analysis by the Nutrition Evaluation Laboratory (NEL) at the HNRCA. A clean catch urine specimen will also be collected for a standard dipstick urinalysis. Pregnancy testing will be conducted for women of childbearing age.

**Intra-Study Laboratory Tests and Procedures:**

Blood specimens will be collected during Parts 1 and 2 of the study on Days 1-2 of each of the cycles at pre- and post-dose of the intervention. All specimens will be sent to the NEL for specimen processing. Approximately 10 mL of whole blood will be collected at baseline, 0.5, 1, 1.5, 2, 2.5, 3, 3.5, 4, 6, 8, 10, 12, and 24 hours post dose during Cycle 1, 2 and 3 for Part 1 and for Part 2 at baseline, 0.5, 1, 1.5, 2, 2.5, 3, 3.5, 4, 6, 8, 10, and 24 hours post dose during Cycle 1 and 2 for measures of Thiamine, TMP, TPP, Metformin and Trimethoprim in plasma and/or RBC at UC Davis.

Urine specimens will be collected at pre-dose void, 0-4, 4-8, 8-12 and 12-24 (home kit) hours for Part 1 and at pre-dose void, 0-4, 4-8, 8-10 and 10-24 (home kit) hours for Part 2 and will be processed by the NEL. Three aliquots will be sent to UCSF and/or UC Davis for measure of Thiamine, TMP, TPP, Metformin and Trimethoprim.

All specimens transferred to UCSF and/or UC Davis will be stripped of all HIPPA identifiers and coded.

**• Collection and Storage of Human Biological Specimens (Tissue Banking)**

Will biological specimens be stored for **future, unspecified**, research?

Yes  No

Optional participation in tissue banking is offered during the informed consent process and an additional signature will be required to consent to tissue banking. Blood and urine samples will be collected during Parts 1 and 2 of the study on Days 1-2 of each of the cycles at pre and post-dose of the intervention.

Tissue Banking will not require an additional blood draw or collection from subjects from that in the main study. The participant will also be informed on how he/she can withdraw his/her sample from the tissue bank if he/she so desires to do so at any time. Participants will be asked to take the time to think about if they wanted to do this, if more time is needed, and will be encouraged to ask any questions or mention any concerns they may have about having their samples stored. All questions will be answered to the participants' satisfaction and any concerns will be addressed accordingly so as to allow participants to give informed consent.

*Types of biological materials to be stored and processed*

Following signing of optional tissue banking consent form, blood samples will be collected according to IRB approved protocol. Tissue banking samples will be stored for an indefinite period for future, unspecified research in a -80C Freezer located in laboratory of the PI. They will be stripped of all HIPPA identifiers and coded. If it is determined that additional analysis of the samples is warranted we will submit the appropriate documents to the IRB. These analyses may include, but are not limited to, genome wide association studies and characterization of metabolites. For these, samples may be distributed to the Nutritional Evaluation Lab, UCSF, UC Davis, or any other collaborators deemed by the principal investigator.

*Measures taken to guard against disclosure of confidential information about the source individual*

- a. The biological materials will be transferred to the tissue bank after they have been de-identified and provided with a unique subject code. Subject codes may be broken at study completion for data analysis or if study subject elects to withdraw from the study.
- b. The master list of the codes will be kept secured electronically (by using a password) and will be filed and locked in a cabinet.
- c. A single designated research technician for each site will be solely responsible for all information related to the de-identification and re-coding of the biological material to be banked. The information will then be transferred to the PI and secured electronically (by using a password) and filed and locked in a cabinet.
- d. If the PI turns the study over to a new PI, the key codes will be transferred to the new PI.
- e. Banked biological material ready to be processed on-site will remain de-identified and coded.
- f. When no further use of the banked biological materials has been established the stored samples will be discarded and the key code destroyed.
- g. We will not go back to the medical record or study volunteer for additional health information. Their contact information at this time is totally useless.

*Withdrawal Consent to banking of biological materials*

At any time after tissue banking permission has been granted. If the study participant wishes to withdraw consent to the research use of biological materials for future studies, after the code has been broken, the samples will be retrieved and destroyed.

## **6 Ethics and Protection of Human Subjects**

### **6.1 Informed Consent Process**

Will subjects be required to provide informed consent?

Yes  No

If Yes, describe the following:

- The consent process will take place in a quiet room of the HNRCA nursing floor. Interested subjects will have as much time as they need to review the informed consent, and will be encouraged to ask any questions. They may also go home and discuss participation with peers or loved ones to ensure they are interested. Screening ICFs will be mailed home prior to their visit to the HNRCA, giving additional time to review it prior to their visit should they choose. They are not expected to bring this consent with them, but rather use it as a reference to prepare for the visit.
- The investigators will follow the SOP: Informed Consent Process for Research (HRP-090).
- Illiterate and non-English speaking subjects will not be enrolled because there are not funds to hire a translator to review the ICF and to translate any safety concerns during the study period. Instructions for the menus and urine collections and food logs would also need to be translated. No direct benefit is expected to come from participation in this study, therefore we do not feel that we are discriminating against illiterate or non-English speakers.

### **6.2 Waiver or Alteration of Consent Process**

N/A

### **6.3 International Research**

N/A

### **6.4 Confidentiality**

Procedures to protect subject confidentiality:

Personal information of subjects who consent to participate in the study will not be given to anyone without permission unless the law requires it. Every effort will be made to keep subjects' information private, but this cannot be totally guaranteed. The Tufts Medical Review Board

(IRB), the HNRCA, the National Institute of Health or study sponsor may check records that identify subjects. These records may include medical or research records and the signed consent form, which will be locked in a locked medical records room at in the HNRCA Volunteer Services Department. Electronic research records will be maintained in a secure, HIPAA compliant REDCap database maintained by the HNRCA Scientific Computing Department with access restricted to essential study personnel only.

All records of subjects that have signed a screening consent, including records of ineligible subjects will be stored for a minimum of 10 years. Only authorized personnel may access the record.

The HNRCA Volunteer Services Department is staffed during normal working hours and is locked during non-working hours. If it is necessary for a medical record to leave the admissions office, it must be signed out only by an HNRCA employee (who is identified by Tufts ID) in a log of the HNRCA ID, name of employee taking possession of the chart, and the date. The records of this study might also be reviewed to make sure all rules and guidelines were followed.

The HNRCA maintains a computerized database of participant information referred to as Protocol Manager (PM), which is a secure Oracle database that is backed up nightly. The database is centralized under the Volunteer Services Department (IRB approved protocol # 6701). Computer access to the database is provided through the Protocol Manager User Interface which was designed as an internal website ("intranet") in order to enable utilization by both PC and Mac users. An electronic gatekeeper (known as a "firewall") blocks all terminals outside of the HNRCA from gaining access. The Scientific Computing Department subscribes to Microsoft's security bulletins and appropriate security updates are applied on an ongoing basis.

If a subject withdraws or is terminated from the study, the study data generated so far will be retained as part of the study database.

Coded blood sample vials collected during the study will be stored without personal identifiers (names, addresses, etc.) at the Nutrition Center until the analyses are completed. Any tissue banking samples will be stored indefinitely at the University of California, San Francisco. Subjects may withdraw consent for DNA storage at any time during or after the study by writing a letter to [name] (School of Pharmacy, Dept. of Bioengineering and Therapeutic Sciences, [name]). All paper study records will be kept in a locked file cabinet and code sheets linking a patient's name to a patient identification number will be stored separately in another locked file cabinet. Only [name] and appointed research staff will have access to this code. Statistical summaries and reports generated for distribution will not contain personal identifiers (names, addresses, etc.)

## **6.5 Provisions to Protect the Privacy Interests of Subjects**

To protect the privacy interest of participants, study procedures (except for meals and blood draws) will be conducted in private testing areas where they can confidentially interact with study personnel. Following informed consent, participants will each be given a unique participant identification number and will never be asked to list their personally identifiable information on study materials or testing software. Access to personally identifiable information (PII) by experimenters will be limited to participants' phone numbers for the purpose of contacting the participant to track compliance and to notify participants of their group assignment at the conclusion of the study, when the randomization code is broken, and participants' addresses for the purpose of mailing compensation. All study data will be coded to avoid the need for further storage or access of PII.

## 6.6 Provisions to Monitor the Study to Ensure the Safety of Subjects

The data will be reviewed, including safety data, adverse events, and efficacy data by the study physician. Research nurses will check in with volunteers at each visit to ensure no changes in health status have occurred. Safety data collection starts at screening and concludes with the final visit in which we reevaluate health status. A data and safety monitoring board will also be put together to assess the study and monitor adverse events as well as safety data periodically.

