#### **4.3 Withdrawal of Subjects**

A subject may be discontinued from either part of the study at any time if the subject, the investigator, or the Sponsor feels that it is not in the subject's best interest to continue. The following is a list of possible reasons for study treatment discontinuation:

- Subject withdrawal of consent
- Subject is not compliant with study procedures or center regulations
- Adverse event that in the opinion of the investigator would be in the best interest of the subject to discontinue study treatment
- Protocol violation requiring discontinuation of study treatment
- Sponsor request for early termination of the study
- Positive pregnancy test (females)

All subjects are free to withdraw from participation at any time, for any reason, specified or unspecified, and without prejudice. However, if a subject is withdrawn or does withdraw from the study, the data collected until that point will still be used in future analyses.

If a subject is withdrawn from treatment due to an adverse event, the subject will be told to follow up with their doctor, contacted to gather information on symptom outcome, and the AE will be reported according to protocol.

Reasonable attempts will be made by the investigator to provide a reason for subject withdrawals. The reason for the subject's withdrawal from the study will be specified in the subject's source documents.

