## 7 Adverse Event Monitoring

### 7.1 Definitions

An adverse event (AE) is any untoward medical occurrence in a human subject, including any abnormal sign (for example, abnormal physical exam or laboratory finding), symptom, or disease, temporally associated with the subject's participation in the research, whether or not considered related to the subject's participation in the research. An AE is therefore any unfavorable and unintended sign (including an abnormal laboratory finding), symptom or disease temporally associated with the administration of an investigational product, whether or not related to that investigational product. An unexpected AE is one of a type not identified in nature, severity, or frequency in the current Investigator's Brochure or of greater severity or frequency than expected based on the information in the Investigator's Brochure.

The Investigator will probe, via discussion with the subject, for the occurrence of AEs during each subject visit and record the information in the site's source documents for both Parts 1 and 2. Adverse events will be recorded in the patient CRF. Adverse events will be described by duration (start and stop dates and times), severity, outcome, treatment and relation to study drug, or if unrelated, the cause.

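### Adverse-event collection closes about 24 hours after the last dose, against roughly 7 to 16 days after earlier doses, and ordinary events still open then have no route to completion

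*Combined protocol and SAP*

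**What the plan says.** - **End of collection.** Section 6.6: "Safety data collection starts at screening and concludes with the final visit in which we reevaluate health status".
- **Which visit that is.** The Part 1 cycle schedule in Section 5.1 is headed "Repeat for a total of three cycles – 9 total visits" and the Part 2 schedule "Repeat for a total of two cycles – 6 total visits". Each cycle ends on Day 2, when subjects "have one more blood collection (24-hour post-dose"). Nothing is scheduled after the last Day 2.
- **Gap between cycles.** Part 2: "There will be two cycles in this study, each separated by at least 5 days". Part 1 has the same minimum with a two-week maximum, and both cycle tables show a washout of 5 to 14 days.
- **Where review is listed.** Both cycle tables list a combined health, medication and adverse-event review on Day -1 to 0 and on Day 1. Neither Day 2 row has it. The Part 2 Day 2 row adds only "Weight, vitals (cycle 2 only").
- **General text.** Section 6.6 has nurses check on volunteers at every visit, Section 7.1 has the investigator ask about adverse events at every visit, and the Schedule of Study Outcomes marks adverse events for visits that span Days 0 to 2.
- **What must be recorded.** Section 7.1: "Adverse events will be described by duration (start and stop dates and times), severity, outcome, treatment and relation to study drug".
- **Follow-up of outcome.** Under Section 4.3, a subject withdrawn for an adverse event is "contacted to gather information on symptom outcome". Section 7.2 requires an evaluation form that includes the outcome for serious and unanticipated events, and has participants report these, with no end date given.

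**The concern.** The design gives every dose except the last a long observation window without planning for it, because the next cycle opens with a review that looks back over the washout. The last dose has no such review. A mild event that begins on the evening after the last Day 2 visit would be recorded after an earlier dose and missed after the last one.

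This matters for two reasons. Section 7.2 obliges the investigator to act if events are more frequent or more severe than expected, and Section 6.6 sets up a board to monitor adverse events. Both rely on counts, and a large share of doses contribute counts from a much shorter window. Second, the data items required by Section 7.1 cannot be completed for an ordinary event that is unresolved when collection closes.

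**Working it through.** **1. Fix how the washout is counted, using the plan's own durations.** Each cycle occupies three days (Day 0, 1, 2). Duration = 3 × cycles + (cycles − 1) × washout.

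| | Washout 5 days | Washout 14 days | Stated in Section 5.1 |
|---|---|---|---|
| Part 1 (3 cycles) | 9 + 2 × 5 = 19 | 9 + 2 × 14 = 37 | 19–37 days |
| Part 2 (2 cycles) | 6 + 5 = 11 | 6 + 14 = 20 | 11–20 days |

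Both ranges are reproduced exactly, so the washout is 5 to 14 full days between Day 2 and the next Day 0.

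**2. Window after an earlier dose.** From dosing on Day 1: one day to Day 2, then the washout, then one day to the next Day 0.
- Next Day 0: 1 + 5 + 1 = 7 days, up to 1 + 14 + 1 = 16 days.
- If the review falls on Day -1: 6 to 15 days.
- If 5 days is instead read as dose to dose, which does not reproduce the stated durations, the minimum is 4 days to Day 0 and 5 days to the Day 1 review.

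**3. Window after the last dose.** Day 1 to Day 2, about 24 hours.

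**4. Share of doses with the short window.** Section 8.3 plans 6 completers in Part 1 and 12 in Part 2.
- All doses: 6 × 3 + 12 × 2 = 18 + 24 = 42.
- Last doses: 6 + 12 = 18, and 18/42 = 43%.
- By part: 6 of 18 (one in three) and 12 of 24 (one in two).
- If all 7 and 14 enrolled subjects reach the last cycle: 21 of 49, again 43%.

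**5. Which treatment comes last (Section 5.1).**
- Part 1: trimethoprim combination in Group 1, thiamine only in Group 2, metformin combination in Group 3.
- Part 2: trimethoprim combination in Group 1, thiamine only in Group 2.

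Within each part, every treatment is last in exactly one sequence.

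**6. Routes to a stop date and outcome after the last Day 2.**
- Withdrawn for an adverse event: contact under Section 4.3.
- Serious or unanticipated event: participant report and evaluation form under Section 7.2.
- Non-serious, anticipated event in a completer: no stated route, whether open on Day 2 or starting later.

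**The case against.** **The tables might be read as leaving no collection at all after the last dose.** The documents do not support that. Section 6.6 describes the final visit as one where health status is reassessed, Sections 6.6 and 7.1 require a check at every visit, and the Schedule of Study Outcomes covers Days 0 to 2. Nor does the order of items in the Day 1 row show that its review is only pre-dose: food is listed after all the blood and urine collections, although it starts at 4 hours. Subjects also stay on site for 12 hours (Part 1) or 10 hours (Part 2) after dosing. The missing Day 2 entry is a table omission to reconcile, and 24 hours is the fair figure.

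**A reader might infer bias against or in favour of trimethoprim.** That does not follow either. The short window rotates across treatments, and Sections 8.1 and 8.2 name no adverse-event endpoint or comparison. Exact balance does depend on group sizes, and seven subjects cannot split equally over three groups, but nothing in the plan points the imbalance toward one treatment.

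**A reader might also conclude that no late event would be followed.** Sections 4.3 and 7.2 cover withdrawals for adverse events and serious or unanticipated events. The gap is confined to ordinary ones.

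**24 hours may be enough.** These are single supervised doses in healthy volunteers, Section 2.2 expects side effects to pass soon after dosing stops, and no passage presents the washout as a safety observation period. This has weight: the documents give no onset times, so the number of events missed cannot be derived. It does not remove the inconsistency, because the plan does record such events for a week or more after its other doses, and Section 7.1 requires completion of every event.

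**Conclusion.** The point holds as a gap in safety ascertainment for the last dose. About 43% of doses are observed for about 24 hours, against about 7 to 16 days for the others. This assumes that adverse events are asked about on Day 2, as the general text implies; that cycle spacing follows the tabulated 5 to 14 days; and that completers number 6 and 12. Separately, the Day 2 rows conflict with Sections 6.6 and 7.1 and the Schedule of Study Outcomes, and Section 7.1 sets a requirement that non-serious, anticipated events open at or starting after the last visit cannot meet. The primary AUC endpoint is unaffected. This is an inexpensive improvement, not a threat to the trial's conclusions.

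**What to change.** 1. Add the health, medication and adverse-event review to the Day 2 row of both cycle schedules, so that they agree with Sections 6.6 and 7.1 and the Schedule of Study Outcomes.
2. Amend Section 6.6 so that adverse-event collection after the last dose runs for at least the minimum interval separating cycles (5 days), closed by one telephone contact.
3. State that events open at that contact are followed to a stop date or outcome.
4. Amend Section 6.5, which limits use of phone numbers to tracking compliance and notifying group assignment, to include adverse-event follow-up.

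The cost is this wording and one short call per subject: at most about 21 (7 + 14), or 14 if Part 1 is already complete, as the opening of the Part 2 text in Section 5.1 suggests. No visit or sample is added.
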